### **6.2.3 Unexpected Adverse Event**

An adverse event is considered “unexpected” when its nature (specificity) or severity is not consistent with applicable product information, such as safety information provided in the protocol or consent.

### **6.3 Toxicity Grading**

The terms “severe” and “serious” are not synonymous. Severity refers to the intensity of an AE (as in mild, moderate, or severe pain); the event itself may be of relatively minor medical significance (such as severe headache). “Serious” is a regulatory definition and is based on patient or event outcome or action criteria usually associated with events that pose a threat to a patient’s life or vital functions. Seriousness (not severity) serves as the guide for defining regulatory reporting obligations.

Toxicity grades are assigned by the study site to indicate the severity of adverse experiences and toxicities using the NCI-CTCAE version 3.0. Toxicity grading for allergic reactions including anaphylaxis is modified from the NCI-CTCAE system to be more appropriate for this study population, and is displayed in Appendix 2. The NCI-CTCAE has been reviewed specifically for this protocol and is otherwise appropriate for this study population. The purpose of using the NCI-CTCAE system is to provide standard language to describe toxicities and to facilitate tabulation and analysis of the data and assessment of the clinical significance of study drug-related toxicities.

Adverse events not included in the CTCAE listing should be recorded and graded 1-5 according to the General Grade Definition provided below:

Grade 1 Mild	Transient or mild discomforts (< 48 hours), no or minimal medical intervention/therapy required, hospitalization not necessary (non-prescription or single-use prescription therapy may be employed to relieve symptoms, e.g., aspirin for simple headache, acetaminophen for post-surgical pain).
Grade 2 Moderate	Mild to moderate limitation in activity some assistance may be needed; no or minimal intervention/therapy required, hospitalization possible.

Grade 3	Severe	Marked limitation in activity, some assistance usually required; medical intervention/therapy required, hospitalization possible.
Grade 4	Life-threatening	Extreme limitation in activity, significant assistance required; significant medical/therapy intervention required, hospitalization or hospice care probable.
Grade 5	Death	Death.

### 6.3.1 Relationship to Procedure Definitions

**Associated:** There is a reasonable possibility that the AE may have been caused by the test product and/or procedure. This definition applies to those adverse events that are considered definitely, probably or possibly related to the procedure.

1. **Definitely related:** An AE that follows a temporal sequence from administration of the test product and/or procedure; follows a known response pattern to the test article and/or procedure; and, when appropriate to the protocol, is confirmed by improvement after stopping the test product (positive rechallenge: and by reappearance of the reaction after repeat exposure [positive rechallenge]); and cannot be reasonably explained by known characteristics of the subject's clinical state or by other therapies.
2. **Probably related:** An AE that follows a reasonable temporal sequence from administration of the test product and/or procedure; follows a known response pattern to the test product and/or procedure, is confirmed by improvement after rechallenge; and cannot be reasonably explained by the known characteristics of the participant's clinical state or other therapies.
3. **Possibly related:** An AE that follows a reasonable temporal; sequence from administration of the test product and/or procedure and follows a known response pattern to the test product and/or procedure, but could have been produced by the participant's clinical state or by other therapies.
4. **Not associated:** An AE for which sufficient information exists to indicate that the etiology is not related to the test product and/or therapy.
5. **Unrelated:** An AE that does not follow a reasonable temporal sequence after administration of the test product and/or procedure and most likely is explained by the participant's clinical disease state or by other therapies. In addition, a negative rechallenge to the test article and/or procedure would support an unrelated relationship.

For additional information and a printable version of the NCI-CTCAE manual, consult the NCI-CTCAE website, <http://ctep.cancer.gov/reporting/ctc.html>.

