#### ***Purpose and Expectations:***

Through Objective #2, we will determine the percentage of adverse events (AE) and serious adverse events (SAE) due to peanut SLIT dosing. There will be a particular focus on symptoms that require treatment and/or hospitalization, symptoms that may lead to poorer compliance, and gastrointestinal symptoms suggestive of eosinophilic disease. We expect that SAEs will be extremely rare. We expect AEs to be more common but to be mostly comprised of transient oropharyngeal itching that does not affect compliance. We expect symptoms of GI and eosinophilic disease to be rare as very little peanut is ingested by the GI route with peanut SLIT

*Objective #3:* To study the changes in immune parameters over time and compare these changes among subjects who were successfully desensitized vs. those who failed. Changes coinciding with the loss of desensitization would also be studied.

*Purpose and Expectations:*

Through Objective #3, we will seek to understand the molecular processes by which SLIT affects the immune system through evaluation of immune mechanisms in relationship to clinical findings of desensitization. We will delineate the impact of peanut SLIT on the subsequent cellular and humoral responses to peanut protein: 1) peanut specific IgE, IgG, and IgG4 response, 2) peanut specific basophil activation, 3) mast cell responses through skin prick testing, and 4) specific T-cell cytokine responses and T regulatory cell (TReg) activation. We anticipate that the effect of peanut SLIT will occur by induction of TRegs, conversion of T cells from an allergic (Th2) to a non-allergic (Th1) lymphocyte response (measured by cytokines, antibody levels, and skin prick test size), a change in peanut-specific basophil activation, or through a combination of the above.

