### **6.1 Procedures and Monitoring**

All unexpected serious adverse events related to the experimental procedures will be reported to the IRB, Food Allergy Initiative DSMB, and FDA in a manner consistent with 21 CFR 312.32. All other adverse events related to the experimental procedures will also be reported to the IRB and DSMB in an expedited manner if they are Grade 3 and above in severity. Any participant deaths that are likely study related and unexpected would be reported within 24 hours. The investigator will continue to follow or obtain documentation of the resolution course of such an event.

Reactions to study drug dosing will be recorded on a dosing log and will not be reported separately as serious adverse events; allergic symptoms are expected during study drug administration and are not unexpected reportable adverse events. Any reaction that meets the criteria for a serious adverse event will be reported both on the dosing log and on an adverse event case report form.

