#### **6.5.1 Notifying the FDA, IRB, and DSMB**

The sponsor will provide the DSMB with listings of all SAEs. Furthermore, the sponsor will inform the FDA, IRB, and DSMB of serious unexpected study-related events.

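### Protocol 6.3.1: all three related grades require a known response pattern that their header does not, so a wholly new type of event fits no grade; separately, the rechallenge criterion is reversed

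*Protocol*

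**What the plan says.** **Causality scale (Protocol 6.3.1).** The header for associated events reads: "There is a reasonable possibility that the AE may have been caused by the test product and/or procedure". The next sentence ties the header to three grades: "This definition applies to those adverse events that are considered definitely, probably or possibly related to the procedure". Each of those grades, *definitely*, *probably* and *possibly related*, then requires a known response pattern. For the weakest, the event must be one that "follows a known response pattern to the test product and/or procedure, but could have been produced by the" child's own condition or other treatment. *Probably related* adds that the event "is confirmed by improvement after rechallenge". The remaining two categories are *not associated*, which needs enough information to show that the product is not the cause, and *unrelated*, which needs the absence of a reasonable temporal sequence.

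**Expectedness (Protocol 6.2.3).** An event is unexpected "when its nature (specificity) or severity is not consistent with applicable product information".

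**Rules that use relatedness.** Protocol 6.1: "All unexpected serious adverse events related to the experimental procedures will be reported to the IRB", and also to the DSMB and FDA. The same section sends other related events to the IRB and DSMB in an expedited manner if they are Grade 3 or above. Protocol 6.5.1: "the sponsor will inform the FDA, IRB, and DSMB of serious unexpected study-related events". Protocol 2.3, rule 1, is triggered by a death related to dosing. For Objective #2, Protocol 2.1 says: "we will determine the percentage of adverse events (AE) and serious adverse events (SAE) due to peanut SLIT dosing".

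**The concern.** A safety reporting rule aimed at unexpected, related events exists chiefly to catch what nobody foresaw. A causality scale that admits an event as related only if its pattern is already known works against that purpose. The header in 6.3.1 sets the right test, but the grades beneath it do not carry it through. An investigator who follows the header and one who follows the grades would classify the same event differently.

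Attribution also matters more here than in a controlled trial. Every child receives open-label SLIT, and the amended design described in SAP Section 1 no longer has two arms. The investigator's causality rating is therefore the only planned means of separating events caused by SLIT from background events.

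The rechallenge wording is a second, independent fault. As written, getting better when the product is given again would count towards a causal link.

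**Working it through.** The point concerns definitions, and the plan gives no figure to reproduce. The check is to run one hypothetical event through the scale and then through the rules that use it.

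**Step 1. The scale.** Take an event with a reasonable temporal sequence after SLIT, no recognised response pattern, and no established other cause.

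| Part of 6.3.1 | Deciding condition | Met? |
|---|---|---|
| Header, *associated* | Reasonable possibility of causation | Yes |
| 1 *Definitely related* | Known response pattern | No |
| 2 *Probably related* | Known response pattern; improvement after rechallenge | No |
| 3 *Possibly related* | Known response pattern; another cause could account for it | No |
| 4 *Not associated* | Information sufficient to say the product is not the cause | No |
| 5 *Unrelated* | No reasonable temporal sequence | No |

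The event satisfies the header and none of the five numbered categories. It is not pushed into *unrelated*; it has no category. The header does not settle the matter, because its second sentence defines its scope through the three grades that the event has just failed.

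**Step 2. Rules that depend on the rating.** If the grades are applied literally, the event carries no related grade and can be missed by:

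- reporting of unexpected related SAEs to the IRB, DSMB and FDA (Protocol 6.1 and 6.5.1);
- expedited reporting of other related events of Grade 3 or above to the IRB and DSMB (6.1);
- stopping rule 1, on deaths (2.3);
- the percentage of AEs and SAEs due to SLIT dosing (2.1, Objective #2).

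**Step 3. Provisions that do not depend on the rating.** The event still enters:

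- the endpoints in Protocol 2.2.2, which count all AEs and SAEs and all gastrointestinal and possible eosinophilic events;
- the listings of all SAEs that go to the DSMB (6.5.1) and the DSMB's review of all AE reports (8.3);
- if it is a death, the requirement in 6.2.2 to report regardless of relationship;
- the passing of all AE information to the IRB (6.5.2).

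Of the two notification provisions that name the FDA, in 6.1 and 6.5.1, both are conditional on relatedness.

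**Step 4. The rechallenge wording.** Three statements in 6.3.1, side by side:

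- *Definitely related* describes improvement after stopping the product but labels it a positive rechallenge. It then uses the same label, correctly, for reappearance on repeat exposure.
- *Probably related* requires improvement after rechallenge.
- *Unrelated* says that a negative rechallenge supports no relationship.

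Improvement on re-exposure is a negative rechallenge. The same observation therefore supports *probably related* under one definition and *unrelated* under another. The text in *definitely related* about stopping the product shows that dechallenge was meant.

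This fault does not cause the gap in Step 1, since *possibly related* has no rechallenge condition. It has its own effect. *Possibly related* presupposes that something else could explain the event. An event of known pattern with no other explanation that falls short of *definitely* is therefore left only with the miswritten *probably*.

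**The case against.** The strongest reply is that this is loose drafting with little practical reach. The header gives the investigator the right test, Protocol 6.4 leaves the determination to the Principal Investigator, and 6.1 and 6.5.1 say related without citing the grades. A sensible investigator would rate a new event with plausible timing as related. This stands in part. A reader might infer from 6.3.1 that such an event can never be rated related, and the documents do not support that. They support a conflict between header and grades, which leaves the outcome to whoever reads them.

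Several further inferences also go too far:

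- *Unexpected and related exclude each other.* They do not. Expectedness is measured against product information, by nature or by severity. A known response pattern is undefined and not tied to that information. A pattern can be known yet unlisted, and a known reaction can be unexpectedly severe.
- *Eosinophilic disease shows the gap.* Protocol 2.1 anticipates symptoms suggestive of it, and 2.2.2 counts possible eosinophilic events regardless of cause. The consent text, which 6.2.3 also names as a source of safety information, is not in the public documents.
- *All stopping rules in 2.3 are compromised.* Rule 2 concerns severe anaphylaxis, a recognised pattern listed in 1.4.1. Rule 3 counts epinephrine use and has no relatedness condition. Only rule 1 is materially exposed.
- *A safety endpoint is biased.* The percentage due to SLIT is purpose text under Objective #2. Neither Protocol 2.2.2 nor the SAP specifies a causality-restricted safety analysis.

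**Conclusion.** The point holds in a limited form. As written, 6.3.1 contradicts itself: its header accepts a reasonable possibility, its grades demand a known pattern, and an event of a wholly new type fits none of the five categories. The rechallenge criterion is reversed and conflicts with the *unrelated* definition. These are faults in operative rules, and they should be corrected.

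The exposure is confined to the four provisions in Step 2 of the working, most clearly FDA notification and expedited Grade 3+ reporting. The incidence endpoints and the DSMB's sight of all SAEs and AE reports are intact.

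No numerical size can be given. It would depend on how many wholly new events occur and on whether they are graded by the header or by the grades, and the documents tell us neither. They also do not show that any event has been misgraded. The conclusion assumes that the grades are applied as worded, that the event has no recognised pattern at all, and that no other cause has been established.

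**What to change.** Four wording changes:

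1. In 6.3.1, make reasonable possibility the operative test: remove the known-pattern condition from *possibly related*, or change it to a known or plausible pattern.
2. State that any AE meeting neither *not associated* nor *unrelated* is graded *possibly related* by default. Change 1 alone is not enough, because *possibly related* still presupposes a candidate other cause.
3. In *probably related*, replace improvement after rechallenge with improvement after stopping (dechallenge). In *definitely related*, relabel the first positive rechallenge as positive dechallenge.
4. In 6.1 and 6.5.1, state that related means definitely, probably or possibly related.

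The cost is small: amended wording in three sections and a check of AEs already graded, to see whether any was left without a grade or rated on the reversed criterion. Treatment, visits and the endpoints do not change. The downside is that slightly more events will be counted as related to SLIT.

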### 6.4 Adverse Events Collection Procedures

The study staff is responsible for collecting and recording all clinical data. As these results are collected, all toxicities and adverse events will be identified and reported to the principal

investigator. Adverse events will be reported as described above. The Principal Investigator will determine relationship of the event to the study intervention and decide course of action for the study participant.

#### **6.4.1 Recording and Reporting Procedures**

Monitoring will be conducted via reports to the DSMB.

#### **6.4.2 SAE Recording and Reporting**

Serious adverse events will be recorded on the appropriate case report forms.

### **6.5 Serious Adverse Event Notification**

The study staff will notify the principal investigator of any serious adverse event immediately upon learning about the event.

#### **6.5.1 Notifying the FDA, IRB, and DSMB**

The sponsor will provide the DSMB with listings of all SAEs. Furthermore, the sponsor will inform the FDA, IRB, and DSMB of serious unexpected study-related events.

#### **6.5.2 Reporting Criteria**

The investigator will ensure the timely dissemination of all AE information, including expedited reports, to the IRB in accordance with applicable local regulations and guidelines.

## **7. MECHANISTIC ASSAYS**

Complementary studies will be performed to measure cellular and humoral immune responses at baseline and longitudinally. These assays have been selected based on hypothesized mechanisms of clinical desensitization induction.

Early data demonstrates that desensitization with peanut SLIT alters both humoral and cellular parameters [23]. We anticipate that peanut SLIT will induce clinical tolerance and SU by either (1) a conversion from a Th2 to Th1 immune response or (2) the induction of TRegs or (3) a combination of both. Subjects will be followed for changes in immunologic parameters at baseline and then yearly with additional studies at the 48 month desensitization DBPCFC and post-avoidance SU DBPCFC. Immunologic assays will focus on peanut specific parameters including: 1) basophil activation and skin prick testing; 2) humoral studies - specific IgE, IgG, IgG4, and IgA; and 3) cellular studies – Treg activation and T cell-stimulated cytokine production.

Briefly, PBMC's will be isolated from blood drawn at yearly time points and cultured with crude peanut extract (CPE)[31], tetanus toxin, and Con A to assess cellular proliferation responses. A control proliferation assay using nonstimulated cells will also be performed. In addition, cultures will be set up to assess cytokine production by PBMC's after stimulation with CPE, tetanus toxin, ConA and control. Culture supernatants will be analyzed yearly for the levels of the following cytokines: IFN- $\gamma$ , IL-4, IL-5, IL-10, IL-13, TGF- $\beta$  and TNF- $\alpha$ . Using flow cytometry, we will determine the presence of TRegs in the blood sample each year. Basophil studies will be performed annually to examine activation markers. Salivary and serum peanut specific antibody levels, including IgE, IgG, IgG4, and IgA will be assessed annually.

### **7.1 Serum specific IgE, IgG, IgG4, and IgA**

Allergen immunotherapy has been shown to induce antigen-specific humoral responses. The balance of isotypic response may play a role in allergen sensitivity (e.g., an increase of IgG/ IgE). We will collect sera at baseline and then yearly with additional studies at the 48 month desensitization DBPCFC and post-avoidance SU DBPCFC. Samples will be stored at  $-80^{\circ}\text{C}$ . Peanut-specific IgE, IgG, IgG4, and IgA levels will be measured using the Phadia ImmunoCAP 100 instrument (Uppsala, Sweden) according to the manufacturer's instructions.

### **7.2 Salivary specific IgA, Secretory-IgA, IgG, IgE, and IgM**

We will utilize ELISA assays to evaluate host antibody responses to Ara h 2 and whole peanut extract in saliva samples collected at the designated time points for serum collection (baseline and then yearly with additional studies at the 48 month desensitization DBPCFC and the post-avoidance SU DBPCFC). Ara h 2 is the major allergen found in peanut. Others have used saliva to measure allergen-specific S-IgA responses in allergic children as well as antigen-specific S-IgA induced in response to oral immunization with KLH (keyhole limpet hemocyanin) or a cholera vaccine. Saliva samples will be tested at an initial dilution of 1:4 followed by serial 2-fold dilutions until we are able to determine an endpoint titer. An endpoint titer will be calculated as the last sample dilution that has an ELISA reading (fluorescent relative light units) 3-fold great than the RLU of the same sample tested against ELISA plates that are not coated with antigen. Once the antigen-specific

endpoint titers are calculated, we will quantitate the total concentration (mcg/ml) of IgG, IgE, IgA, Secretory-IgA and IgM in each saliva sample and report the antigen-specific responses as a “titer/mcg of total antibody”.

### **7.3 Cytokine measurements**

Isolated PBMCs from baseline and then yearly with additional studies at the 48 month desensitization DBPCFC and the post-avoidance SU DBPCFC will be cultured in RPMI 1640 containing 10% fetal bovine serum, 1% penicillin/streptomycin, and 1% glutamine. Cells will be cultured in 24 well plates ( $4 \times 10^6$ /well/ml) in the presence or absence of CPE (200 mcg/ml), tetanus toxin (5 mcg/ml), or Con A (5 mcg/ml). Supernatants will be collected after 72hrs of culture and aliquots will be stored at  $-80^\circ\text{C}$  until analyzed. IFN- $\gamma$ , IL-4, IL-5, IL-13, IL-10, TGF- $\beta$ , and TNF- $\alpha$  levels will be determined either by ELISA according to the manufacturer’s instructions (R&D systems, Minneapolis) or by a Cytokine Bead Array (BD). The stimulated cells will be collected to isolate RNA which will be used to measure GATA-3, T-bet, Foxp3, and Th2 cytokines by qPCR.

### **7.4 TReg assay**

Isolated PBMCs from baseline and then yearly with additional studies at the 48 month desensitization DBPCFC and the post-avoidance SU DBPCFC will be cultured with CPE (200 mcg/ml) or media alone and incubated for 7 days. Cells will be surface stained for CD4 and CD25, then intracellularly stained for FoxP3. The presence of TRegs will be assessed by flow cytometry (CD25+/CD4+/Foxp3+).

### **7.5 Basophil Activation Assay**

Whole blood from baseline and then yearly with additional studies at the final randomly selected post-avoidance DBPCFC will be divided and stimulated in the presence of IL-3 with several dilutions of peanut antigen ( $10^0$  mcg/ml,  $10^{-1}$  mcg/ml,  $10^{-2}$  mcg/ml,  $10^{-3}$  mcg/ml), anti-IgE (1mcg/ml), and media alone. After 30 minutes incubation, RBCs will be lysed and leukocytes will be fixed and stored frozen for batch mAb staining and flow cytometric analysis of activation markers. Basophils will be identified as CD123+ CD203c+ lin (CD3, CD14, CD19, CD41) events and activation will be assessed by CD203c (ENPP3) and CD63 (LAMP-3), which are markers for piecemeal and classical degranulation, respectively.

